4.4 Interim Analysis

Interim analysis was removed after amendment. The reason for this was a very steep increase of patients' recruitment over last weeks before interim analysis. Therefore, even if the interim analysis resolution would have been to stop the study, all screened patients would have already completed the study per the protocol. So, conduct of the interim analysis would have been futile.

4.5 Data Safety Monitoring Board

Not applicable.

4.6 Safety Management Team

Not applicable.

5. DESCRIPTION OF NON-STANDARD DATA COLLECTED AND DERIVED VARIABLES

5.1 Other Non-Standard Baseline Characteristics

Not applicable.

5.2 Non-Standard Disease History

Not applicable.

5.3 Efficacy data

The efficacy data collected are:

Efficacy data collected in the study are: assessment of pain abdominal pain and bloating/flatulence intensity as measured by NRS-11 scale.

5.4 Non-standard Safety Data

The following non-standard safety data are collected: *Exposure*.

5.5 Drug Accountability and Exposure

Drug accountability and exposure variables collected in the study is: number of tablets per day.

Drug accountability and exposure variables calculated during the analysis are: sum dose of study drug (mg), duration of taken study drug (days), average dose taken per day (mg), compliance.

6. FURTHER SPECIFICATIONS TO THE STANDARD ANALYSES IN MODULE 2

6.1 Trial Design [2]

6.1.1 Trial Periods

	Screening and run-in period	Treatment Period	Follow up
Mebeverine + Simethicone	Screening (Days -21 - 1)	Investigational Treatment (Days 1-29)	Follow up (Day 36)
Duspatalin	Screening (Days -21 - 1)	Investigational Treatment (Days 1-29)	Follow up (Day 36)
Espumisan	Screening (Days -21 - 1)	Investigational Treatment (Days 1-29)	Follow up (Day 36)

6.1.2 Trial Elements

Trial Element	Description of Element	Rule for Start of Element	Rule for End of Element	Planned Duration of Element
Screen	Screening and Randomization	Informed consent obtained	First dose of treatment	
Treatment "Mebeverine+ Simethicone"	Investigational Treatment of taken study drug "Mebeverine + Simethicone"	First administration of "Mebeverine + Simethicone"	6 days after first administration of "Mebeverine + Simethicone"	7 days
Treatment "Duspatalin"	Investigational Treatment of taken study drug "Duspatalin"	First administration of "Duspatalin"	6 days after first administration of "Duspatalin"	7 days
Treatment "Espumisan"	Investigational Treatment of taken study drug "Espumisan"	First administration of "Espumisan"	6 days after first administration of "Espumisan"	7 days
FOLLOW UP	Follow-up period	Date of last study drug administration	Last Contact with Subject	1 day

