3.3.3. Visit 3, End of study treatment (Week 4, Day 29)

Duration of study treatment is 4 weeks.

On Visit 3 (Week 4, Day 29) the abdominal pain and bloating/flatulence intensities registration according to the Patient Diary will be checked by investigator, as well as the frequency and consistency of stool, drotaverin intake, and the adverse events and concomitant medications. Physical examination, vital signs, and body weight will be assessed, blood and urine for haematology and biochemistry tests and urinalysis will be sampled. Patients will assess their quality of life by completing IBSQOL. At this visit study treatment will be completed and patients will receive recommendations for further treatment of abdominal functional disorder.

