5.2. Administration of the study drug and randomization

At the visit 2 Week 0, Day 1, all eligible patients will be randomized into three equal groups (1:1:1):

- Mebeverine+Simethicone, 135 mg+80 mg, three times a day during 4 weeks
- Duspatalin® 135 mg three times a day during 4 weeks
- Espumisan®, 80 mg three times a day during 4 weeks

Patients will take the study drugs during 4 weeks: Mebeverine+Simethicone 1 tablet three times a day before meal, Duspatali® 1 tablet three times a day before meal, Espumisan ® 2 capsules 3 times a day after or before meal.

The last dose has to be taken at the evening before the Visit 3 (Week 4, Day 29).

The patients will register the study drug administration in the diary.

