4.3 Safety analysis

The Safety subject sample will be used for the analysis of the safety data. In addition to this, three treatment groups will be used: "Mebeverine+Simethicone fixed-dose combination", "Espumisan® (simethicone)" and "Duspatalin® (mebeverin)".

The gap period is 7 days for adverse events, 7 days for vital signs, laboratory measurements and concomitant medications.

The following dictionaries are used for coding of medical terms:

Medical term	Dictionary	Version
Concomitant medications	WHO DDE	March 2020, or later
Adverse events	MedDRA	23.1
Medical histories	MedDRA	23.1

Treatment Emergent Adverse Events

An AE that starts during a unique treatment or that already exists before the start of that unique treatment but worsens during the treatment or post-treatment period (if no longer than 7 days after last dose of respective treatment) will be considered as treatment emergent for that unique treatment.

The following unique treatments are distinguished: Mebeverine + Simethicone, 135 mg+80 mg, three times a day; Duspatalin 135 mg three times a day; Espumisan, 80 mg (2 capsules 40 mg) three times a day. AEs will be reported on a per-subject basis, i.e., counting subjects rather than events. This means that if a subject suffers the same AEs repeatedly during the applicable study or treatment period, the event will be counted only once for that period. Repeated events per subject will be summarized according to the following rule: if a subject suffered the same AE more than once, the event will be assigned the worst severity, the closest relationship to the study drug and the earliest starting date. Only treatment emergent AEs (TEAE) will be reported. In the listings, however, all occurrences of the AEs will be presented.

For each unique treatment, TEAES will be summarized by MedDRA primary system organ class (SOC), high level term (HLT) within primary SOC and preferred term (PT) within HLT and primary SOC. Severity and drug-event relationship of adverse events are summarized separately.

In the listings, all occurrences of AEs will be presented together with all relevant information from the eCRFs. In addition, TEAEs will be flagged. Start and end day of the AE and the day of last dose of study drug will be also presented, relative to the start day of the treatment under which is started or worsened and relative to start of any study drug.

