4.3.10 Drug Accountability, Treatment Compliance and Exposure

Source: DAT001, DAL001, NST005, NSL04

The patient should take the first study drug dose at the Visit 2 day (Week 0). During telephone contact (TC 1, Week 2, Day 0), the Investigator checks the patient's treatment compliance and whether he/she follows the recommendations on the Patient's Diary filling, and, if necessary, conducts an additional conversation with the patient about the proper drug administration and filling out the Patient's Diary. At Visit 3 (Week 4, Day 29), the patient should return all used and unused study drug packagings. The Investigator will check compliance with the recommendations for study drug self-administration at Visit 3 (Week 4, Day 29) based on the results of accounting for the returned study drug and the patient's diary.

The study drug compliance will be calculated at Visit 3 using the formula:

Compliance = (N dispensed. – N returned.) / N calc. * 100%

where N dispensed. = number of tablets/capsules dispensed, N returned. = number of tablets/capsules returned, N calc. = estimated number of tablets/capsules the volunteer was to receive since the previous visit.

The calculated percentage compliance will be categorized as:

- Too Low: < 80% compliance.
- Adequate: $\geq 80\%$ to $\leq 120\%$ compliance.
- Too High: > 120% compliance.

Sum dose of study drug (mg), duration of taken study drug (days) and average dose taken per day (mg) will be calculated for each subject. Data is collected in **patient diaries**.

Duration of taken study drug (days) will be calculated as sum of days where at least one dose were taken by subject.

Average dose taken per day (mg) will be calculated with the following formula:

Average dose taken per day (mg) = $\frac{\text{Sum dose of study drug (mg)}}{\text{Duration of taken study drug (days)}}$

All data of drug accountability, treatment compliance and exposure will be presented in subject data listings and by-treatment group tables.

4.3.11 Compliance with selection criteria assessments.

Source: NSL006, NSL007, NSL008, NSL009

Pregnancy test, test for HIV, hepatitis B and C, feces analysis for fecal calprotectin and colonoscopy results will be listed only.

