6.1.4 Unique Treatments

The trial arms for this study are made up of the following unique treatments:

Unique trea	tment		Elements				
Description	Label	Arm	Screen	Treatment "Mebeveri ne + Simethicon e"	Treatment "Duspatali n"	Treatment "Espumisa n"	FOLLO W UP
Mebeverine + Simethicone, 135 mg+80 mg, three times a day	Mebeveri ne + Simethico ne	Mebeveri ne + Simethic one	Screening and Randomizat ion	Investigatio nal Treatment of taken study drug "Mebeveri ne + Simethicon e"	_	_	Follow- up period
DuspatalinDuspata in-	al						

Duspatalin 135 mg three times a day	Duspata lin	Duspata lin	Screening and Randomizat ion	_	Investigatio nal Treatment of taken study drug "Duspatali n"	_	Follow- up period
Espumisan, 80 mg (2 capsules 40 mg) three times a day	Espumis an	Espumis an	Screening and Randomizat ion	_	_	Investigatio nal Treatment of taken study drug "Espumisa n"	Follow- up period

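### SAP 6.1.2 ends each treatment element on Day 7 of a four-week treatment, so most treatment days fall in no element and adverse event tables built on element dates would omit them

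*SAP*

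**What the plan says.** - **SAP 6.1.2 (Trial Elements).** Each treatment element starts at first administration and ends "6 days after first administration of" the arm's drug. The planned duration is 7 days, and all three rows read alike. The follow-up element starts at "Date of last study drug administration", ends at the last contact with the subject, and has a planned duration of 1 day.
- **SAP 6.1.1 (Trial Periods).** Every arm shows "Investigational Treatment (Days 1-29" as its treatment period, with follow-up at Day 36.
- **SAP 6.1.4 (Unique Treatments).** "The trial arms for this study are made up of the following unique treatments", followed by a grid that sets each unique treatment against the screening element, its own treatment element and the follow-up element.
- **SAP 4.3 (Safety analysis).** The treatment-emergent definition begins "An AE that starts during a unique treatment or that already exists before the start of that unique treatment" and goes on to worsening during treatment or up to 7 days after the last dose. Summary tables are limited to treatment-emergent events; the listings show every event.
- **SAP 4.3.7.** Events that start after the last administration but within the gap period also count towards the treatment period.
- **Protocol 3.3.3.** "Duration of study treatment is 4 weeks".

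**The concern.** SAP section 6 gives the study-specific settings for the standard analyses, so its element table is an instruction that a programmer may follow. As written, it closes treatment after one week of a four-week regimen. Follow-up does not open until the last dose, which leaves a stretch of dosing days with no element.

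This matters for safety. The treatment-emergent definition depends on an event starting or worsening within a unique treatment, and the unique treatments are laid out by these elements. If the tables were built from element dates, an event starting on Day 15, for example, would be in a listing but not in the incidence, severity or relationship tables. The incidence and severity of adverse events is among the trial's stated secondary objectives.

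**Working it through.** This is a day count; no power or sample-size formula applies.

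**Inputs**
- First dose on Day 1. SAP 4.3.10: "The patient should take the first study drug dose at the Visit 2 day (Week 0". Visit 2 is Day 1.
- Treatment element ends at first dose + 6 days, planned duration 7 days (SAP 6.1.2).
- Follow-up element starts on the day of the last dose, L (SAP 6.1.2).
- Protocol timing: L = 28. Protocol 5.2: "The last dose has to be taken at the evening before the Visit 3 (Week 4, Day 29".
- SAP 6.1.5 timing: L = 29, because the table ties the date of last administration to relative day 29, with a window of 1 day either side.
- Post-treatment gap for adverse events: 7 days (SAP 4.3).

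**Step 1: reproduce the plan's figure.** The end day is 1 + 6 = 7, and the length is 7 − 1 + 1 = 7 days. The end rule and the planned duration agree in all three rows, so this is not one mistyped cell.

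**Step 2: days in no element.** These run from Day 8 to Day L − 1. The count is L − 8 and the share of dosing days is (L − 8)/L.
- L = 28 (protocol): Days 8 to 27, 20/28 = 71%.
- L = 29 (SAP 6.1.5): Days 8 to 28, 21/29 = 72%.
- With the visit window, L can be 27 (19/27 = 70%) or 30 (22/30 = 73%).

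**Step 3: close of the treatment-emergent window.**
- From dose dates: L + 7 = Day 35 (L = 28) or Day 36 (L = 29).
- If the 7-day gap were counted from the end of the element instead: 7 + 7 = Day 14. SAP 4.3 counts the gap from the last dose, so this version conflicts with the text. It shows how far apart the two anchors are.

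**Step 4: an element that covers treatment.** It would span 28 days (ending 27 days after first administration) under the protocol's timing, or 29 days (ending 28 days after) under SAP 6.1.1. An end rule tied to the last administration removes the gap either way.

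**Step 5: look for support elsewhere.** Nothing else in either document describes a 7-day treatment element. The 7-day gap period in SAP 4.3 is a separate window after the last dose.

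**The case against.** The strongest reply is that the rule deciding which events are treatment-emergent does not cite 6.1.2. SAP 4.3 names the unique treatments by regimen, without element dates. It measures the post-treatment window from the last dose, which presupposes that treatment runs until then. SAP 4.3.7 attributes events to the treatment period, and SAP 6.1.1 sets that period at Days 1 to 29. Together these give a coherent window from first dose to last dose plus 7 days. The grid in 6.1.4 also includes the screening element; taken as a date rule it would place screening events within a unique treatment, which cannot be intended.

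Most of this stands. It shows that a correct derivation is available and better supported, so the loss of events is a risk and not a certainty. It does not remove the contradiction. The 7-days-after-last-dose wording in 4.3 sits in the clause on worsening, and 4.3.7 deals with events starting after the last administration. Neither states that a new event in mid-treatment falls within the unique treatment. Detailed handling is referred to Module 2, which is not among the documents, so which dates the programs use cannot be confirmed.

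It is also fair that no event would vanish from the report. The listings carry all occurrences, flag the treatment-emergent ones and show start day against last-dose day, and serious events are listed separately.

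The 1-day planned duration for follow-up has no shown analytic effect, because that element has its own start and end rules. It needs tidying only.

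**Conclusion.** The contradiction is real. SAP 6.1.2 cannot be reconciled with SAP 6.1.1 or with the protocol's four weeks, and read literally it leaves 71% to 72% of dosing days in no element. The consequence is conditional: treatment-emergent tables built on element dates would omit events starting in most of Weeks 2 to 4, and tables built on dose dates would be correct.

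Three stronger readings are tempting, and the documents do not support them.
- A reader might infer that the safety tables will understate harm. That requires element dates to be used, which nothing in the documents establishes and which 4.3, 4.3.7 and 6.1.1 point away from.
- A reader might put the unassigned share at 21/28 = 75%. That takes the gap from a Day 29 last dose and the denominator from a Day 28 one.
- A reader might estimate that about 60% of onsets would be lost (21/35). That combines the same two timings and assumes onsets spread evenly over treatment and the gap period, which no text supports.

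Primary efficacy is untouched, because SAP 4.2.1 sets its assessment windows separately. Severity is minor to moderate: a consistency error in a specification table, with a plausible route into the safety tables and a very cheap correction.

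**What to change.** 1. In SAP 6.1.2, end each treatment element at the date of last study drug administration, and start the follow-up element on the following day so that no day belongs to both.
2. Reconcile the planned durations in 6.1.2 (treatment, and the 1-day follow-up entry against the protocol's one-week follow-up) with 6.1.1, 6.1.5 and the protocol. This includes settling whether the SAP's last dosing day is Day 28 or Day 29, since the sources differ by a day.
3. In SAP 4.3, state that the treatment-emergent window runs from first dose to last dose plus the 7-day gap, for new events as well as worsening ones.
4. Check that Module 2 and the adverse event programs use the same dates.

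The cost is a few lines in 6.1.2 and 4.3, with alignment of 6.1.1 or 6.1.5 where the last day differs, and a short check of the programs. Treatment, data collection, sample size and the primary analysis do not change.

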6.1.3 Trial Arms

	Elements								
Trial Arm	Screen	Treatment "Mebeverine + Simethicone"	Treatment "Duspatalin"	Treatment "Espumisan"	FOLLOW UP				
Mebeverine + Simethicone	Screening and Randomization	Investigational Treatment of taken study drug "Mebeverine + Simethicone"	_	_	Follow- up period				
Duspatalin	Screening and Randomization	_	Investigational Treatment of taken study drug "Duspatalin"	_	Follow- up period				
Espumisan	Screening and Randomization	-	_	Investigational Treatment of taken study drug "Espumisan"	Follow- up period				

6.1.4 Unique Treatments

The trial arms for this study are made up of the following unique treatments:

Unique trea	tment		Elements				
Description	Label	Arm	Screen	Treatment "Mebeveri ne + Simethicon e"	Treatment "Duspatali n"	Treatment "Espumisa n"	FOLLO W UP
Mebeverine + Simethicone, 135 mg+80 mg, three times a day	Mebeveri ne + Simethico ne	Mebeveri ne + Simethic one	Screening and Randomizat ion	Investigatio nal Treatment of taken study drug "Mebeveri ne + Simethicon e"	_	_	Follow- up period
DuspatalinDuspata in-	al						

Duspatalin 135 mg three times a day	Duspata lin	Duspata lin	Screening and Randomizat ion	_	Investigatio nal Treatment of taken study drug "Duspatali n"	_	Follow- up period
Espumisan, 80 mg (2 capsules 40 mg) three times a day	Espumis an	Espumis an	Screening and Randomizat ion	_	_	Investigatio nal Treatment of taken study drug "Espumisa n"	Follow- up period

6.1.5 Visits and related definitions

Test / Examination	Visit name	Visit Label	Visit Number	Reference Start Date/Time	Relative Day Number
Informed Consent Form, patient registration	Screening	Screening	1	Date of Informed consent obtained	-217
Demography, medical history	Screening	Screening	1	Date of Informed consent obtained	-217
	Screening	Screening	1	Date of Informed consent obtained	-217
Weight, Height (screening only), BMI	Visit 1	Visit 1 (week 0)	2	Date of first Drug Adminitration	1
	Visit 3 (End of Trial)	Visit 3 End of Trial or Early Discantinuation visit	4	Date of last Drug Administration	29 (+-1)

Test / Examination	Visit name	Visit Label	Visit Number	Reference Start Date/Time	Relative Day Number
Physical	Screening	Screening	1	Date of Informed consent obtained	-217
examination	Visit 3 (End of Trial)	Visit 3 End of Trial or Early Discantinuation visit	4	Date of last Drug Administration	29 (+-1)
	Screening	Screening	1	Date of Informed consent obtained	-217
Vital signs	Visit	Visit 1 (week 0)	2	Date of first Drug Adminitration	1
	Visit 3 (End of Trial)	Visit 3 End of Trial or Early Discantinuation visit	4	Date of last Drug Administration	29 (+-1)
Hematology	Screening	Screening	1	Date of Informed consent obtained	-217
	Visit 3 (End of Trial)	Visit 3 End of Trial or Early Discantinuation visit	4	Date of last Drug Administration	29 (+-1)
Biochemistry	Screening	Screening	1	Date of Informed consent obtained	-217
	Visit 3 (End of Trial)	Visit 3 End of Trial or Early Discantinuation visit	4	Date of last Drug Administration	29 (+-1)

Test / Examination	Visit name	Visit Label	Visit Number	Reference Start Date/Time	Relative Day Number
Pregnancy test	Screening	Screening	1	Date of Informed consent obtained	-217
Urinalysis	Screening	Screening	1	Date of Informed consent obtained	-217
	Visit 3 (End of Trial)	Visit 3 End of Trial or Early Discantinuation visit	4	Date of last Drug Administration	29 (+-1)
Tests for HIV, hepatitis B and C	Screening	Screening	1	Date of Informed consent obtained	-217
Feces analysis for fecal calprotectin	Screening	Screening	1	Date of Informed consent obtained	-217
Colonoscopy	Screening	Screening	1	Date of Informed consent obtained	-217
ECG	Screening	Screening	1	Date of Informed consent obtained	-217
Randomization	Visit 1	Visit 1 (week 0)	2	Date of first Drug Administration	1
Abdominal pain intensity on the NRS-11 scale	Screening	Screening	1	Date of Informed consent obtained	-217

Test / Examination	Visit name	Visit Label	Visit Number	Reference Start Date/Time	Relative Day Number
	Visit 1	Visit 1 (week 0)	2	Date of first Drug Administration	1
	Visit 2 (Telephone Call)	Visit 2 (Telephone Call)	3	Date of Telephone Call	15 (+-1)
	Visit 3 (End of Trial)	Visit 3 End of Trial or Early Discantinuation visit	4	Date of last Drug Administration	29 (+-1)
	Screening	Screening	1	Date of Informed consent obtained	-217
Flatulence intensity on the NRS-11 scale	Visit 1	Visit 1 (week 0)	2	Date of first Drug Adminitration	1
	Visit 2 (Telephone Call)	Visit 2 (Telephone Call)	3	Date of Telephone Call	15 (+-1)
	Visit 3 (End of Trial)	Visit 3 End of Trial or Early Discantinuation visit	4	Date of last Drug Administration	29 (+-1)
Stool frequency	Screening	Screening	1	Date of Informed consent obtained	-217
	Visit 1	Visit 1 (week 0)	2	Date of first Drug Adminitration	1
	Visit 2 (Telephone Call)	Visit 2 (Telephone Call)	3	Date of Telephone Call	15 (+-1)

Test / Examination	Visit name	Visit Label	Visit Number	Reference Start Date/Time	Relative Day Number
	Visit 3 (End of Trial)	Visit 3 End of Trial or Early Discantinuation visit	4	Date of last Drug Administration	29 (+-1)
Bristol stool scale	Screening	Screening	1	Date of Informed consent obtained	-217
	Visit 1	Visit 1 (week 0)	2	Date of first Drug Adminitration	1
	Visit 2 (Telephone Call)	Visit 2 (Telephone Call)	3	Date of Telephone Call	15 (+-1)
	Visit 3 (End of Trial)	Visit 3 End of Trial or Early Discantinuation visit	4	Date of last Drug Administration	29 (+-1)
Patient diary distribution	Screening	Screening	1	Date of Informed consent obtained	-217
	Visit 1	Visit 1 (week 0)	2	Date of first Drug Adminitration	1
Patient diary assessment	Visit 1	Visit 1 (week 0)	2	Date of first Drug Adminitration	1
	Visit 2 (Telephone Call)	Visit 2 (Telephone Call)	3	Date of Telephone Call	15 (+-1)
	Visit 3 (End of Trial)	Visit 3 End of Trial or Early Discantinuation visit	4	Date of last Drug Administration	29 (+-1)

Test / Examination	Visit name	Visit Label	Visit Number	Reference Start Date/Time	Relative Day Number
Evaluate the quality of life (IBSQOL questionnaire)	Visit 1	Visit 1 (week 0)	2	Date of first Drug Adminitration	1
	Visit 3 (End of Trial)	Visit 3 End of Trial or Early Discantinuation visit	4	Date of last Drug Administration	29 (+-1)
Study drug dispense	Visit 1	Visit 1 (week 0)	2	Date of first Drug Adminitration	1
Study drug accountability and compliance assessment	Visit 3 (End of Trial)	Visit 3 End of Trial or Early Discantinuation visit	4	Date of last Drug Administration	29 (+-1)
Study drug return	Visit 3 (End of Trial)	Visit 3 End of Trial or Early Discontinuation visit	4	Date of last Drug Administration	29 (+-1)
Adverse events	Screening	Screening	1	Date of Informed consent obtained	-217
	Visit 1	Visit 1 (week 0)	2	Date of first Drug Adminitration	1
	Visit 2 (Telephone Call)	Visit 2 (Telephone Call)	3	Date of Telephone Call	15 (+-1)
	Visit 3 (End of Trial)	Visit 3 End of Trial or Early Discantinuation visit	4	Date of last Drug Administration	29 (+-1)
	Follow up	Follow up	5	Date of Follow up	36 (+1)

Test / Examination	Visit name	Visit Label	Visit Number	Reference Start Date/Time	Relative Day Number
Concomitant medications	Screening	Screening	1	Date of Informed consent obtained	-217
	Visit 1	Visit 1 (week 0)	2	Date of first Drug Adminitration	1
	Visit 2 (Telephone Call)	Visit 2 (Telephone Call)	3	Date of Telephone Call	15 (+-1)
	Visit 3 (End of Trial)	Visit 3 End of Trial or Early Discantinuation visit	4	Date of last Drug Administration	29 (+-1)
	Follow up	Follow up	5	Date of Follow up	36 (+1)

6.2 Further Specifications to the Standard Tables in Module 2

Not applicable

